**6.9 3-, 6-, 12-, and 24-Month Telephone Assessments**

Subjects receive a telephone assessment for adverse events, including serious adverse events and the new onset of chronic diseases at 3, 6, and 12 months; and an assessment of pre-existing conditions, serious adverse events and the new onset of chronic diseases at 24 months after completion of study treatment with RBX2660. These phone calls must occur within the window specified in Table 6-1; calls [REDACTED]

The assessment of pre-existing conditions includes discussion with the subject to determine if the condition improved, unchanged, worsened or resolved since completion of study treatment. Information on concomitant medications is updated as needed. [REDACTED]

[REDACTED] Adverse events and the new onset of chronic diseases are to be recorded and reported as required in Section 7.0 [REDACTED]

[REDACTED] The last phone call occurs at 24 months after completion of study treatment with RBX2660. [REDACTED]

### 6.10 Antibiotic-treated Historical Control

The efficacy of RBX2660 will be evaluated by comparing the recurrence-free rate observed in the study population to the recurrence-free rate identified from antibiotic-treated historical controls. A chart review will be conducted by Rebiotix or its designees to gather the historical control data to be used in the comparison. The historical control protocol can be found in Appendix 1 to this study protocol.

## 7.0 Assessment of Safety and Efficacy

### 7.1 Assessment of Safety

#### 7.1.1 Definitions

- Adverse event: an adverse event (AE) is any untoward medical occurrence associated with the use of RBX2660, whether or not the event is considered product-related.
- Adverse reaction: Any adverse event caused by RBX2660.
- Suspected adverse reaction (SAR): any adverse event for which there is a reasonable possibility that RBX2660 caused the adverse event. “Reasonable possibility” means there is evidence to suggest a causal relationship between the RBX2660 and the adverse event. Suspected adverse reaction implies a lesser degree of certainty about causality than “adverse reaction,” which means any adverse event caused by RBX2660.
- Serious adverse event (SAE) or serious suspected adverse reaction: An adverse event or suspected adverse reaction is considered “serious” if, in the view of either the investigator, Medical Monitor or sponsor, it results in any of the following outcomes:
  - Death
  - Life-threatening adverse event
  - Inpatient hospitalization  $\geq$  24 hours or prolongation of an existing hospitalization

- Persistent or significant incapacity or substantial disruption of the ability to conduct normal life functions
- Congenital anomaly/birth defect.

Important medical events that do not result in death, are not life-threatening, or do not require hospitalization may be considered serious when, based upon appropriate medical judgment, they may jeopardize the subject and may require medical or surgical intervention to prevent one of the outcomes listed in this definition.

- Unexpected adverse event or unexpected suspected adverse reaction: an adverse event or suspected adverse reaction is considered “unexpected” if it is not listed in the Investigator’s Brochure or is not listed at the specificity or severity that has been observed.
- Life-threatening: An adverse event or suspected adverse reaction that places the subject at immediate risk of death. It does not include an AE or SAR that, had it occurred in a more severe form, might have caused death.

#### 7.1.2 Anticipated Adverse Events

The following is list of anticipated adverse events that may or may not be causally related to RBX2660, the enema procedure, or CDI:

- gas (flatulence)
- belching
- abdominal distension or bloating
- increased diarrhea
- abdominal cramping or pain
- constipation
- colitis
- fever  $\geq 38.0^{\circ}\text{C}$  ( $100.4^{\circ}\text{F}$ )
- fatigue
- chills
- transmission of disease from the donor to recipient
- rectal irritation or pain
- rectal bleeding
- nausea
- vomiting
- hypotension
- puncture of the intestine

### 7.1.3 Solicited Adverse Events

The following list of anticipated adverse events are solicited from subjects via the Subject Diary from the date of enrollment through the 7th day after completing study treatment:

- gas (flatulence)
- abdominal distension or bloating
- rectal irritation or pain
- chills/severe shivering
- abdominal pain or cramping
- increased diarrhea
- constipation
- rectal bleeding
- nausea
- vomiting
- fever  $\geq 38.0^{\circ}\text{C}$  ( $100.4^{\circ}\text{F}$ )

Through the completion of the Subject Diary, subjects are asked specific questions regarding frequency and severity of the solicited AEs.

### 7.1.4 Preexisting Condition

A preexisting condition, including abnormal physical exam findings, is one that is present at the start of the study and is to be recorded at the time of the screening or baseline visits. A preexisting condition is to be recorded as an adverse event if the frequency, intensity or the character of the condition worsens during study participation. They are also to be assessed at the 3-, 6-, 12-, and 24-month telephone assessments; See Section 6.9.

### 7.1.5 Adverse Event Reporting to the Sponsor

Sites are required to record and report all adverse events to Rebiotix via entry on the Adverse Event eCRF in the study database within **ten (10)** working days of discovery unless it is an SAE or serious suspected adverse reaction. Serious adverse events (SAEs) and serious suspected adverse reaction events must be reported within **three (3)** working days of discovery by recording them in the study database. Adverse event information is collected from the time the subject signs the Informed Consent Form and HIPAA Form (if applicable) through study termination. All adverse events, including serious adverse events and the new onset of chronic diseases, will be collected through 12 months; serious adverse

events and the new onset of chronic diseases will be collected through 24 months after completion of study treatment. [REDACTED]

[REDACTED]  
[REDACTED]  
[REDACTED] Neither a condition, hospitalization, prolonged hospitalization, nor surgery are reported as an adverse event if the hospitalization or prolonged hospitalization is for diagnostic or elective surgical procedures for a preexisting condition. Surgery should not be reported as an outcome of an adverse event if the purpose of the surgery was elective or diagnostic and the outcome was uneventful. Reoccurrence of CDI is *not* to be reported as an AE or SAE unless hospitalization  $\geq 24$  hours is required to treat it. If hospitalization is not required, it is to be recorded on the Follow-up eCRF and CDI History and On-study Episodes eCRF and reviewed as a component of efficacy assessment. If hospitalization for recurrent CDI is required, it is to be reported as an SAE within 3 working days of discovery in the database and on the CDI History and On-study Episodes eCRF. [REDACTED]

#### 7.1.6 Grading Adverse Event Severity

Adverse Events are to be graded by severity by the site investigator; see Section 7.1.8. For the classification of adverse events, severity is not the same as serious, which is defined in section 7.1.1. Severity is an indication of the *intensity* or a specific event (e.g., mild, moderate or severe). Classification of an event as serious relates to an event's outcome or intervention criteria and is usually associated with events that pose a threat to a subject's life or functioning. An event can be severe but not serious, such as a migraine. [REDACTED] the site investigator will categorize the severity of an adverse event on the AE eCRF.

**Table 7-1: Severity Grading Table\***

Parameter	Grade 1: Mild	Grade 2: Moderate	Grade 3: Severe	Grade 4: Potentially Life-threatening
Flatulence	Symptoms causing no or minimal interference with usual social and functional activities	Symptoms causing greater than minimal interference with usual social and functional activities	NA	NA
Belching (burping)	Symptoms causing no or minimal interference with usual social and functional activities	Symptoms causing greater than minimal interference with usual social and functional activities	NA	NA
Abdominal distension or bloating	Symptoms causing no or minimal interference with usual social and functional activities	Symptoms causing greater than minimal interference with usual social and functional activities	Symptoms causing inability to perform usual social and functional activities	NA

Parameter	Grade 1: Mild	Grade 2: Moderate	Grade 3: Severe	Grade 4: Potentially Life-threatening
Increased diarrhea	Increase of $\leq 3$ stools over baseline per 24-hour period	Increase of 4 – 6 stools over baseline per 24-hour period	Bloody diarrhea if not present at baseline OR increase of $\geq 7$ stools over baseline per 24-hour period OR IV fluid replacement indicated if not indicated at baseline	Life-threatening consequences, e.g., hypotensive shock
Abdominal cramping/pain	Discomfort/pain causing no or minimal interference with usual social and functional activities	Discomfort/pain causing greater than minimal interference with usual social and functional activities	Discomfort/pain causing inability to perform usual social and functional activities	Disabling pain causing inability to perform basic self-care OR inpatient hospitalization $\geq 24$ hours
Constipation	Occasional or intermittent symptoms, occasional use of stool softeners, laxatives, dietary modifications or enema	Persistent symptoms with regular use of laxatives or enemas indicated	Symptoms causing inability to perform usual social and/or functional activities	Life-threatening consequences, e.g., obstruction, toxic megacolon
Colitis	No symptoms, regardless of pathologic or radiographic evidence of inflammation	Abdominal pain, mucus or blood in the stool	Abdominal pain, fever, change in bowel habits with ileus; peritoneal signs	Life-threatening consequences, e.g., perforation, bleeding, ischemia, necrosis, toxic megacolon

Parameter	Grade 1: Mild	Grade 2: Moderate	Grade 3: Severe	Grade 4: Potentially Life-threatening
Fever	37.7 – 38.6°C (99.9 – 101.5° F)	38.7 – 39.3°C (101.6 – 102.8° F)	39.4 – 40.5°C (102.9 – 104.9° F)	> 40.5°C (104.9° F)
Fatigue/malaise	Symptoms causing no or minimal interference with usual social and functional activities	Symptoms causing greater than minimal interference with usual social and functional activities	Symptoms causing inability to perform usual social and functional activities	Incapacitating fatigue/malaise symptoms causing inability to perform basic self-care functions
Chills	Symptoms causing no or minimal interference with usual social and functional activities	Symptoms causing greater than minimal interference with usual social and functional activities	Symptoms causing inability to perform usual social and functional activities	NA
Rectal discomfort or irritation	No symptoms or symptoms not requiring medical intervention	Symptomatic with medical intervention (topical medications / treatments) indicated	Symptoms causing inability to perform usual social and functional activities or requiring medical intervention other than topical medications / treatments	NA
Rectal bleeding	Mild or intermittent without transfusion	Persistent without transfusion	Requires transfusion	Life-threatening consequences

Parameter	Grade 1: Mild	Grade 2: Moderate	Grade 3: Severe	Grade 4: Potentially Life-threatening
Nausea	Transient ( $\leq 24$ hours) or intermittent nausea with nor or minimal interference with oral intake	Persistent nausea resulting in decreased intake for 24-48 hours	Persistent nausea resulting in decreased intake $> 48$ hours OR aggressive rehydration indicated, e.g., IV fluids	Life-threatening consequence, e.g., hypotensive shock
Vomiting	Transient ( $\leq 24$ hours) or intermittent vomiting with nor or minimal interference with oral intake	Frequent episodes of vomiting with no or mild dehydration	Persistent vomiting resulting in orthostatic hypotension OR aggressive rehydration indicated, e.g., IV fluids	Life-threatening consequence, e.g., hypotensive shock
Hypotension	NA	Symptomatic, corrected with oral fluid replacement	Symptomatic, IV fluids indicated	Shock requiring use of vasopressors or mechanical assistance to maintain blood pressure

Parameter	Grade 1: Mild	Grade 2: Moderate	Grade 3: Severe	Grade 4: Potentially Life-threatening
Adverse event not identified elsewhere in this table	Symptoms causing no or minimal interference with usual social and functional activities	Symptoms causing greater than minimal interference with usual social and functional activities	Symptoms causing inability to perform usual social and functional activities	Symptoms causing inability to perform basic self-care functions OR medical or operative intervention indicated to prevent permanent impairment, persistent disability, or death

\*Adapted from *Division of AIDS Table for Grading of Severity of Adult and Pediatric Adverse Events and Addendum 3: Rectal Grading Table for Use in Microbicide Studies; May 2012.*

**7.1.7 Causality**

For all adverse events, the investigator must pursue and obtain adequate information to determine the outcome of the adverse event and to assess whether the AE meets the criteria for classification as an SAE, serious suspected adverse reaction, suspected adverse reaction, unexpected adverse event, or unexpected suspected adverse reaction. For all adverse events, sufficient information should be obtained by the investigator to determine the causality of the adverse event. For adverse events with a causal relationship to the RBX2660 or the enema procedure, follow-up by the investigator is required until the event or its sequelae resolve or stabilize at a level acceptable to the investigator.

The Investigator will make a causality assessment for all AEs and decide whether there is a reasonable possibility that the AE may have been caused by the study product or procedure, including an assessment of biologic plausibility, presence or absence of alternative causal explanations (such as continuation or exacerbation of the subject’s

recurrent CDI symptoms), and temporal relationship to product administration and/or the procedure. Relatedness to RBX2660 or the enema procedure is defined as:

Unrelated: The event is due to an underlying or concurrent illness or effect of concomitant therapy and is not related to the study product or procedure (e.g., has no temporal relationship to study product or procedure, or has a much more likely alternative etiology).

Possible: There is some temporal relationship between the event and the administration of the study product or procedure, and the event is less likely to be explained by the subject's medical condition or other therapies.

Probable: The temporal relationship between the event and administration of the study product or procedure is suggestive, and the event is unlikely to be explained by the subject's medical condition or other therapies.

Definite: The event follows a reasonable temporal sequence from administration of the study product or procedure, follows a known or suspected response pattern to the study product and/or procedure, improves upon stopping the study product, and reappears upon repeated exposure, if that occurs.

[REDACTED]

#### 7.1.8 Medical Monitor

An independent Medical Monitor reviews SAEs and adverse events of interest to provide an objective, qualified judgment of the events. The Medical Monitor is a physician not participating as an investigator in this study. The Medical Monitor has the responsibility to review and evaluate the information relevant to product safety throughout the development and implementation of the protocol. The Medical Monitor performs the following functions:

- Reviews and adjudicates SAEs and AEs of interest;
- Reviews the study protocol and Investigator's Brochure for adequacy of safety oversight;

### 7.1.10 Sponsor Reporting of Adverse Events

The study sponsor is required to report certain study events in an expedited fashion to FDA and Health Canada. These written notifications of adverse events are referred to as expedited safety reports.

#### 7.1.11.1 Temporal Reporting Requirements

The following describes the expedited safety reporting requirements by timeline for reporting and associated type of event:

- **Within 7 calendar days of event discovery by Rebiotix**  
Rebiotix will notify FDA and Health Canada of any unexpected fatal or life-threatening suspected adverse reaction as soon as possible but in no case later than seven calendar days after the sponsor's initial receipt of the information.
- **Within 15 calendar days of event discovery by Rebiotix**  
Any study event that is:
  - suspected adverse reaction
  - serious
  - unexpectedThe AE must meet all three of these criteria for expedited reporting.

#### 7.1.11.2 Additional Reporting Requirements

The sponsor will identify in IND safety reports all previous reports concerning similar adverse events and analyze the significance of the current event in light of the previous reports.

#### 7.1.11.3 Reporting AEs to FDA and Health Canada

Rebiotix will report adverse events to FDA and Health Canada as required by applicable regulations. All adverse events will be reported in the annual and final clinical study reports.

## 7.2 Assessment of Efficacy

The primary efficacy parameter is treatment success, defined as the absence of CDI diarrhea without the need for retreatment with *C. difficile* anti-infective

therapy or FT through 56 days after the completion of study treatment (Visit 3). Some subjects may continue to have short bouts of diarrhea before the 56-day time point, but most if not all will be resolved within 30 days after receiving RBX2660. The efficacy assessment will occur at the 8-week office visit.

[REDACTED]  
[REDACTED]  
[REDACTED]

[REDACTED] See Sections 6.10 and 8.0 of this protocol and the separate Statistical Analysis Plan for additional details on the efficacy assessment.

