**3.5 Definition of Treatment Success**

Treatment success is defined as: the absence of CDI diarrhea without the need for retreatment with *C. difficile* anti-infective therapy or FT through 56 days after completion of study treatment.

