### 3.7 Management of Treatment Failures

Treatment failures (as determined by the site investigator at the time of CDI recurrence) are to be treated with the therapy(ies) deemed most appropriate by their study investigator. All CDIs, including reoccurrences and new episodes, are to be captured in detail on the CDI History and On-study Episodes eCRF.

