### 3.9 Blinding

This is an open-label study; no blinding will be employed.

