**6.8 8-Week Office Visit (Visit 4)**

Subjects return to the study site for the 8-week follow-up visit after completing study treatment with RBX2660. [REDACTED]

[REDACTED] At this visit, reoccurrence of CDI and adverse event information is assessed, a review of medication changes and pre-existing conditions is conducted, and the SF-36 Form is administered. The assessment of pre-existing conditions includes discussion with the subject to determine if the condition is improved, unchanged, worsened or resolved since completion of study treatment. The Subject Diary is collected and reviewed with the subject. [REDACTED] If CDI reoccurrence is suspected < 56 days after completing study treatment, the investigator assesses for recurrence using the four criteria in Section 3.6. The need for retreatment for *C. difficile* infection in the absence of a positive stool test for *C. difficile* will be made by the study investigator so that the appropriate treatment of the subject can be quickly administered in the case of failure to avoid serious adverse events, including hospitalization or death. If the subject does not have reoccurrence of CDI before 56 days after completing study treatment, s/he is considered a treatment success (see Section 3.5). [REDACTED]

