4.1.2 Definition of CDI Diarrhea

Clostridium difficile diarrhea is defined as the passage of ≥ 3 watery stools in 24 or fewer consecutive hours for at least two consecutive days.

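### Protocol 3.5, 3.6 and 6.8 do not classify an untested or unretreated CDI-diarrhea episode the same way, and the unqualified sentence in 7.2 aggravates the gap

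*Protocol*

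**What the plan says.** - **CDI diarrhea** (Protocol 3.4, SAP 4.1.2) is clinical only: three or more "watery stools in 24 or fewer consecutive hours for at least two consecutive days". No stool test is part of it.
- **Success** (Protocol 3.5, SAP 4.1.3) is "the absence of CDI diarrhea without the need for retreatment with" anti-infective therapy or fecal transplant through day 56.
- **Failure** (Protocol 3.6, SAP 4.1.4) needs four criteria together: CDI diarrhea before day 56, a positive stool test, a need for retreatment, and no other cause.
- **Default at week 8** (Protocol 6.8): "If the subject does not have reoccurrence of CDI before 56 days after completing study treatment, s/he is considered a treatment success", followed by a reference to 3.5. The four criteria are applied when the investigator suspects a recurrence.
- **Expectation of diarrhea** (Protocol 7.2): "Some subjects may continue to have short bouts of diarrhea before the 56-day time point, but most if not all will be resolved"; the time it gives is 30 days from receipt of RBX2660. It then says: "The efficacy assessment will occur at the 8-week office visit".
- **Who decides**: the site investigator (Protocol 3.8, SAP 4.1.6), and "This is an open-label study; no blinding will be employed" (Protocol 3.9).

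**The concern.** Success and failure are not complements. Success is lost as soon as the stool-count definition is met, but failure is reached only when a test result and a retreatment decision are added. A subject can fall between the two, and the visible text does not say how that subject counts in the primary endpoint.

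Section 6.8 turns on recurrence of CDI, the label that Section 3.6 gives to failure. An investigator who reads it that way can score an in-between subject a success. An investigator who follows its reference to 3.5 cannot. Two sites could score the same episode differently.

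Section 7.2 bears on this judgment. It tells unblinded investigators to expect short bouts of diarrhea without saying that the bouts meant are those below the 3.4 threshold. The primary endpoint is compared with historical controls, so any leniency in scoring the RBX2660 arm goes straight into its success rate.

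**Working it through.** **Step 1. Put the definitions side by side.** Take an episode before day 56 that meets 3.4, with no other cause found.

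| Episode | Success under 3.5? | Failure under 3.6? | Result under 6.8 |
|---|---|---|---|
| Positive test, retreatment needed | No | Yes | Failure |
| Not tested, not retreated | No | No | Success if not regarded as a recurrence; not a success if 3.5 is followed |
| Positive test, retreatment not needed | No | No (third criterion) | Same ambiguity |
| Not tested, retreated | No | No (second criterion) | Foreseen, but no visible scoring rule |

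The last row is not hypothetical. Section 6.8 lets the investigator decide on retreatment without a positive test. SAP 6.3 removes from the Per Protocol Population subjects who had a fecal transplant before the 8-week follow-up without a documented recurrence. The plan thus anticipates in-between cases, but the visible text does not say how they score in the primary analysis, which uses the Evaluable Population. The third row shows that a stool test alone would not close the gap, because an episode not needing retreatment still misses 3.6.

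**Step 2. Check the visible sensitivity analysis.** SAP 8.7.1 imputes missing responses as successes. An in-between subject scored as a success is not missing, so that analysis does not test this scoring.

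**Step 3. Size.** The plan gives no figure to reproduce: the visible text shows no alpha, power or assumed rates.

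- One subject at the enrolment ceiling (Protocol 8.1): 1/150 = 0.67 points. With fewer evaluable subjects each weighs more; at 100 it is 1/100 = 1.0 point.
- Assume that 3%, 5% or 10% of subjects have such an episode scored as success: 0.03, 0.05 or 0.10 × 150 = 4.5, 7.5 or 15 subjects. Against 3.5 read literally, the rate is 3, 5 or 10 points too high.
- Assume instead that only 30–60% of these episodes are true recurrences: 0.03 × 0.30 = 0.9 points, up to 0.10 × 0.60 = 6 points.

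**Step 4. What that could do to a test, for scale only.** Assumptions: 150 treated and 100 controls (SAP 4.5); no true difference; 35% recurrence-free in both groups (1 − 0.65, from the recurrence rate after two relapses in Appendix 1, A3); pooled two-proportion z-test at two-sided 0.05; controls scored without error; a share m of treated subjects wrongly scored as success.

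P(falsely significant in favor of RBX2660) = Φ[(m − 1.96·SE₀)/SE₁], where SE₀ is the pooled and SE₁ the unpooled standard error.

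For m = 5%:
- pooled rate = (150 × 0.40 + 100 × 0.35)/250 = 0.38
- SE₀ = √[0.38 × 0.62 × (1/150 + 1/100)] = 0.0627
- SE₁ = √(0.40 × 0.60/150 + 0.35 × 0.65/100) = 0.0622
- result = Φ(−1.17) = 12.1%

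| m | 0 | 2% | 5% | 10% |
|---|---|---|---|---|
| P | 2.5% | 5.0% | 12.1% | 34.8% |

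Under the same assumptions, an observed difference of about 12.6 points is needed for p < 0.05. The documents do not give m, so this is not a finding about the trial.

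**The case against.** The case against a stronger reading is good, and most of it stands.

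- **Section 7.2 does not tell anyone to ignore an episode.** A reader might infer that bouts clear up on their own or may go untested. The text says neither. It uses plain diarrhea just after the defined term, so the natural reading keeps the two apart. What remains is that this limit is not written down.
- **Detection is not confined to week 8.** A reader might infer that early bouts are missed because efficacy is assessed at the 8-week visit. But calls in weeks 1–4 ask about recurrence (6.7), subjects are told to call if symptoms return (6.5, 6.6), the SAP schedule marks recurrence assessment at every visit from Visit 2 and at every call, and stool is requested at weeks 1, 4 and 8 and at recurrence (6.4.1). These steps find episodes; they do not say how one is classified.
- **Sections 7.2 and 3.7 do not conflict.** Section 3.7 covers "Treatment failures (as determined by the site investigator at the time of CDI recurrence". Failure can be declared when it happens, while success through day 56 can only be confirmed at about week 8. Section 3.2 is equally compatible.
- **Section 6.8 points to 3.5.** An investigator who follows the reference would not score such an episode a success. This weakens the default but does not remove it, because the sentence itself turns on recurrence, which is the 3.6 concept.
- **Controls are not shown to face a stricter rule.** Appendix 1, A4 defines recurrence in order to identify charts, and no control outcome rule is visible. Charts may also miss brief untreated diarrhea, which would raise the control rate. The net direction of bias is therefore not established.
- **Redaction.** Text is blacked out in Protocol 3.6, 6.7, 6.8 and 7.2 and in SAP 4.1.4, 4.1.6 and 8.7.1. A testing or indeterminate-outcome rule may be there, so its absence cannot be asserted.

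**Conclusion.** The point holds in a limited form. On the visible text, an episode that meets 3.4 before day 56 but is untested or not retreated is not a success under 3.5, is not a failure under 3.6, and can be scored a success through 6.8. That is a mismatch between definitions. The sentence in 7.2 aggravates it for unblinded investigators but is not its source.

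The size is unknown. The only firm figure is about 0.67 points per misclassified subject at n = 150. The ranges of 3–10 and 0.9–6 points, and the false-significance figures, rest on assumed shares, an assumed alpha and error-free scoring of controls. The conclusion also assumes that the redacted text holds no rule for these episodes. If it does, the remaining defect is only that 6.8 and 7.2 do not visibly refer to it.

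**What to change.** 1. **Protocol 7.2.** Limit the sentence on short bouts to diarrhea that does not meet Section 3.4. State that an episode meeting 3.4 through day 56 is assessed against 3.6 when it occurs, and that the 8-week visit confirms the outcome.
2. **Protocol 3.5, 3.6 and 6.8, and SAP 4.1.3, 4.1.4 and 4.1.6.** Reconcile these so that every 3.4 episode lacking a stool result or retreatment has one stated classification for the primary endpoint. If a redacted rule already does this, add a cross-reference to it in 6.8 and 7.2.
3. **SAP 8.7.1.** List every episode meeting SAP 4.1.2 with its test status and result and its retreatment status. Add a sensitivity analysis that counts episodes missing the four failure criteria because they were untested or not retreated as not recurrence-free.

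The cost is wording in both documents, one listing and one extra analysis. The reported RBX2660 success rate may be lower under the new classification or the sensitivity analysis. The change concerns how outcomes are classified and does not alter how any subject is treated.
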